10.7 Analyses of Exploratory Endpoints

Graphical summaries of changes from baseline over time in biomarker levels may be provided. Association between baseline levels or presence of tumor biomarkers will be explored graphically for objective response and PD effects. If evident, correlation analyses for changes in biomarkers and tumor response or progression free survival will be performed.

10.8 Pharmacokinetic or Pharmacokinetic/Pharmacodynamic Endpoints

AMG 211 serum concentration-time data will be used to determine the PK parameters using non-compartmental methods and will be listed for individual subjects. The following parameter will be estimated: C_{ss} , calculated as average concentration between achievement of plateau and EOI. Only in cycle 1 the following parameters will be estimated: $t_{1/2}$ and AUC_{inf} . Other parameters such as CL and V_{ss} may be estimated. Post dose serum concentrations below the lower limit of quantifications (BLQ) will be set to missing for non-compartmental analysis or 1/2 BQL for potential population PK analysis while those at predose will be set to zero. Actual dosing and sampling time will be used for PK analysis. The reasons for excluding any sample from the analyses will be provided. Other types of analysis such as compartmental modeling and population PK may be performed if necessary dependent on the data. The result of additional analysis may be reported separately from the clinical study report (CSR).

Individual concentration-time data will be tabulated and presented graphically. Mean concentration-time profiles for each dose will be provided using scheduled time. PK parameters will be summarized for each dose level using descriptive statistics, including subject numbers, means, standard deviations, medians, minimums, and maximums.

For dose proportionality analyses, C_{ss} will be dose normalized and log transformed prior to analysis. A linear regression may be performed using $\ln(C_{ss})$ as the dependent variable and $\ln(\text{dose})$ as the independent variable. The scatter plots will show these estimated curves as well as the 90% confidence region around these curves. Tables will be generated to show the parameter estimates as well as the 90% confidence interval for the slope of the model. Given the broad dose range included in this study, the dose proportionality analyses may be restricted to the dose range being considered for the next stage of development.

PK/PD modeling may be performed if data are adequate to explore the relationship between AMG 211 exposure and various PD endpoints.

10.9 Changes from Protocol-Specified Analyses

There are no changes to the protocol-specified analyses.

11. LIST OF PLANNED TABLES, FIGURES AND LISTINGS [TFLs]

The definitive list of TFLs to be produced for this study is documented in the Programme Index.

13. PRIORITIZATION OF ANALYSES

There is no prioritization of analyses.

14. DATA NOT COVERED BY THIS PLAN

Exploratory data not included in this plan may be analyzed at a later date or may be analyzed by a different Amgen Department.

15. APPENDICES

Appendix A. Technical Detail and Supplemental Information Regarding Statistical Procedures and Programs

Imputation Rules for Partial or Missing Stop Dates

If the month and year are present, impute the last day of the month. If only the year is present, impute December 31 of that year. If the stop date is entirely missing, assume the event or medication is ongoing. If a partial or complete stop date is present and the 'ongoing' or 'continuing' box is checked, then it will be assumed that the AE or conmed stopped and the stop date will be imputed, if partial.

Imputation Rules for Partial or Missing Start Dates

		Stop Date							
		Complete: yyyymmdd		Partial: yyyymm		Partial: yyyy		Missing	
Start Date		<1 st Dose	≥1 st Dose	<1 st Dose yyyymm	≥1 st Dose yyyymm	<1 st Dose yyyy	≥1 st Dose yyyy		
Partial: yyyymm	=1 st Dose yyyymm	2	1	2	1	N/A	1	1	
	≠ 1 st Dose yyyymm		2		2	2	2	2	
Partial: yyyy	=1 st Dose yyyy	3	1	3	1	N/A	1	1	
	≠ 1 st Dose yyyy		3		3	3	3	3	
Missing		4	1	4	1	4	1	1	

1 = Impute the date of first dose

2 = Impute the first of the month

[figure not shown]
3 = Impute January 1 of the year

4 = Impute January 1 of the stop year

Note: For subjects who were never treated (first dose date is missing), partial start dates will be set to the first day of the partial month.

Note: If the start date imputation leads to a start date that is after the stop date, then do not impute the start date.

CCI

Appendix C. Toxicity Probability Interval (TPI) Bayesian Design

The dose-escalation cohorts will use a TPI Bayesian design to guide dose escalation. The MTD target TPI for DLT is (0.20, 0.35), and TPIs of (0.35, 0.60) and (0.60, 1.00) are defined as excessive and unacceptable, respectively. The design seeks to identify a dose most likely to have a DLT rate in the target TPI, but with overdose control that limits the possibility that the dose has an excessive or unacceptable DLT rate (Babb et al, 1998). The probability of a DLT at dose level d_i is assumed to follow a Bernoulli distribution with probability p_i where the logit of p_i increases linearly with the log of the standardized dose in the following 2-parameter logistic model:

$$\log [p_i / (1-p_i)] = \text{logit}(p_i) = \log[a] + \exp(\log[b]) \log (d_i / d_{\max})$$

where a and b are random variables and d_{\max} is the maximum planned dose.

A minimally informative prior distribution (Neuenschwander et al, 2008) was selected for $\theta = (\log a, \log b)$ where the probability that the true DLT rate is ≤ 0.60 at the lowest dose (200 $\mu\text{g}/\text{day}$ for 7 days) is 0.90 and the probability the true DLT rate is ≤ 0.20 at the maximum dose (6400 $\mu\text{g}/\text{day}$ for 14 days) is 0.21. Median values for p_i were interpolated per the logistic model. For each d_i , 2 quantiles for p_i were selected from a Beta distribution with the target median and a precision < 2 . This set of quantiles fully specified a target prior for θ . A bivariate normal distribution for θ was assumed where $(\log a)$ has a normal distribution with mean ma and standard deviation sa , and $(\log b)$ has a normal distribution with mean mb and standard deviation sb , and r is the correlation between $(\log a)$ and $(\log b)$. Numerical integration was used to calculate $\text{Pr}[p_i \leq q(d_i)]$, where $q(d_i)$ is a quantile for dose d_i . An optimal bivariate normal distribution was estimated that achieved the minimum sum of squared difference between achieved and specified quantiles across all doses. The bivariate normal distribution prior solution has $ma = 0.0536$, $sa = 1.685$, $mb = -0.1469$, $sb = 1.001$, and $r = -0.216$.

The operating characteristics of the TPI Bayesian design were evaluated via simulation. The cohort size was fixed to be 3 subjects. All simulated studies started with an initial dose of 200 $\mu\text{g}/\text{day}$ for 7 days and subsequent doses were selected based on the rules specified in [Section 8](#).

The design was evaluated for two possible dose-response scenarios consistent with the design's model: "Low" and "High" MTDs. The target MTD of these 2 scenarios are set to be 1/3, and this target was set at a dose of 400 $\mu\text{g}/\text{day}$ for 14 days, and 3200 $\mu\text{g}/\text{day}$ for 14 days for the Low High scenarios, respectively. An "acceptable" final dose was defined as one with the

highest or second highest target TPI probability and a less than 0.25 excessive or unacceptable TPI probability. The acceptable doses by scenario were 200, 400 for Low and 1600, 3200 for High. The bivariate normal distribution for each scenario was estimated as per the prior. A Bernoulli probability for each subject in the simulations was selected from a random sample for the bivariate normal distribution for a given scenario, and a random DLT outcome for the subject was generated based on this DLT probability.

The simulation results are summarized in the table below. The average sample size increased from 15.7 to 20.8 in Low to High MTD scenarios. Early DLTs resulted in close to 5% chance of stopping with no dose selection in both cases due to the over-dose control criteria. The average Low and High final dose was about 360 and 1600 µg/d. The rate of acceptable dose selection is higher in Low scenario (83.1%), comparing with High scenario (51.4%). The average number of DLTs and DLT rate is higher in Low scenario than High scenario due to early occurrence of DLTs.

Simulation Results of TPI Model

	Low Acceptable Dose: 200, 400	High Acceptable Dose: 1600, 3200
Number of Subjects (IQR)	15.7 (15, 18)	20.8 (18, 24)
Acceptable Rate (95% CI)	83.1% (80.6%, 85.4%)	51.4% (48.3%, 54.5%)
No Dose Rate (95% CI)	4.5% (3.3%, 6.0%)	3.7% (2.6%, 5.1%)
Dose (IQR)	358.0 (200, 400)	1583.8 (800, 1600)
Number of DLTs (IQR)	3.8 (2, 4)	3.1 (2, 4)
DLT Rate	24.1%	15.0%

CI = confidence interval; DLT = dose-limiting toxicity; IQR = interquartile range

Appendix D. DLRM Outputs List

Listings:

1. subject demographics
2. date, time, dose of investigational product administration
3. electrocardiogram (ECG) results, change from baseline
4. vital signs
5. reported adverse events (AEs)
6. safety laboratory data (chemistry, hematology, Urinalysis, coagulation)
7. medical history
8. concomitant medications
9. prior chemotherapy data

Figures

1. line plot of vital signs by time course
2. line plot of all safety labs by time course
3. line plot of ECGs results by time course
4. DLT probability plot at each dose [TPI design if DLT is observed]

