In total, four patients (2 at 3 mg and 2 at 7.5 mg + dexamethasone) experienced DLTs: hypoxia (n=2), diarrhea (n=1), and cytokine release syndrome (CRS; n=1). The MTD was determined to be MEDI-565 5 mg with dexamethasone premedication. The most common treatment-emergent adverse events were nausea, abdominal pain, vomiting, and fatigue. Grade 3 treatment-related adverse events were observed in 5 patients and included diarrhea, CRS, increased alanine aminotransferase, hypertension (all, n=1), and hypoxia (n=2). Six serious treatment-related adverse events were reported in 5 patients and included diarrhea, vomiting, pyrexia, CRS (all, 1 event), and hypoxia (2 events). Five patients were discontinued from treatment because of adverse events, including diarrhea, CRS, and central nervous system metastases (all, n=1), and hypoxia (n=2).

Nineteen patients (48.7%) had ADAs; 5 (12.8%) had high titers, 2 with decreased MEDI-565/AMG 211 concentrations. No objective responses occurred; 11 (28%) had stable disease as best response

Study 20130354 (phase 1) is the ongoing Phase 1 study evaluating the safety, tolerability, pharmacokinetics, pharmacodynamics, and efficacy of AMG 211 administered as continuous intravenous infusion (cIV) in subjects with relapsed/refractory gastrointestinal adenocarcinoma. As of April 2016, approximately 32 subjects received AMG 211 for up to 6400 µg/cIV without any DLT.

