5.1 Treatment Assignment

An Amgen representative will notify the site(s) in writing when a cohort is open to screen new subjects. In the dose-escalation cohorts, subjects will be assigned sequentially into cohorts as they open. Three subjects will initially be enrolled into each dose-escalation cohort with at least a 48-hour interval between treatment start of subject 1 and subject 2 of each cohort. In the event that a DLT is observed, 3 additional subjects may be enrolled for a total of up to 6 evaluable subjects. Subjects are considered evaluable, for the purposes of the dose level review of safety information if they receive at least 90% of the planned doses of investigational product or if they have discontinued investigational product due to a DLT. Subsequent cohorts will begin enrollment upon completion of the previous cohort if it is deemed safe to proceed to the next dose level.

Subjects not participating in the Imaging Study will start enrollment into the dose-expansion cohort upon completion of the dose-escalation cohorts. Subjects concurrently participating in the Imaging Study will start enrollment into the dose-expansion cohort while dose-escalation cohorts are still open for enrollment.

The treatment start date is to be documented in the subject's medical record and on the enrollment eCRF.

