10.3.1 Interim Analyses

The DLRT (see [Section 10.3.2](#)) is responsible for all dose level decisions during dose escalation. Dose decisions are planned after every 3 to 6 subjects are enrolled throughout the dose-escalation cohorts. The DLRT considers the recommendation for subsequent doses based on the following rules:

- Based on the modified TPI Bayesian model, the next dose is the one with the highest probability of the target TPI (0.20, 0.35), but with a less than 0.25 probability of an excessive or unacceptable TPI.
- If ≥ 1 subject has a DLT at a dose level, then dose escalation cannot occur unless there are 6 or more DLT-evaluable subjects at that dose level. However, if a transient cytokine-release syndrome is reported as the DLT, but resolves within

48 hours and can be managed with prophylactic corticosteroids, the DLRT may decide to escalate the dose with the institution of prophylactic corticosteroid administration.

- The maximum allowed dose increase will be 1 dose level above the maximum of previous evaluated doses.
- Dose escalation can be achieved by evaluating a higher dose level with the same infusion duration (eg, 800 µg/day for 14 days to 1600 µg/day for 14 days), or by evaluating the same dose level with a prolonged infusion duration (eg, from 800 µg/day for 14 days to 800 µg/day for 28 days). The DLRT may also decide to explore in parallel both options mentioned above after the dose-escalation decision is made, or to prioritize one schedule. In this case, 2 TPI models may be run in parallel to obtain dose recommendations for these 2 schedules separately.
- Intermediate dose levels not pre-specified may be considered based on the optimal dose recommended by the TPI model.

The DLRT is responsible for making the decision to end dose escalation. Generally, the DLRT may consider the dose escalation complete if 1 of the following rules is met:

- The highest planned dose level is evaluated and no DLTs occur at any dose level. In this case the maximum administered dose will be used in a dose-expansion cohort.
- The TPI Bayesian model recommends the same dose 3 times (not necessarily sequentially).
- A total of approximately 39 DLT-evaluable subjects have been enrolled.

The Amgen Medical Monitor and Amgen Global Safety Officer can make dose decisions without convening the DRLT in the following limited circumstances:

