10.4.2 Primary Endpoint

A modified TPI Bayesian model will be used in the dose-escalation cohorts to estimate the MTD based on the incidence of DLTs among DLT-evaluable subjects that occur during the DLT window. Refer to [Appendix E](#) for details of the TPI Bayesian model. The MTD target TPI is (0.20, 0.35), and TPIs of (0.35, 0.60) and (0.60, 1.00) are defined as excessive and unacceptable, respectively. After each cohort, the model's recommended MTD dose for evaluation is the dose with the highest probability of the target TPI, but with a less than 0.25 probability of an excessive or unacceptable TPI. Dose-expansion will enroll additional subjects to gain further clinical experience. A final model estimate of the MTD using AMG 211 cIV dosing will be obtained utilizing all DLT-evaluable subjects from the dose-escalation cohort. Subjects who are not AMG 211 naïve at the time of enrollment will not be DLT-evaluable. Dose expansion-cohort subjects who participated in the Imaging Study are not DLT-eligible and will be excluded from this analysis. The probability of each TPI and of a DLT will be summarized by dose along with the estimated dose-toxicity curve. In addition, a sensitivity analysis will be done using data from all subjects in both dose-escalation and dose-expansion cohorts who receive at least 90% of the planned doses of investigational product during Cycle 1.

Additional summaries and/or models may be investigated, if warranted, to evaluate DLTs or other safety outcomes overall or in relation to dose, for example, all or selected related treatment-emergent adverse events leading to treatment interruption and/or discontinuation by cycle of onset.

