8. INTERIM ANALYSIS AND EARLY STOPPING GUIDELINES

Dose decision analyses are planned after every 3 to 6 DLT-evaluable subjects are enrolled throughout the dose-escalation cohorts. The DLRT considers the recommendation for subsequent doses based on the following rules:

- Based on the modified TPI Bayesian model ([Bailey et al, 2009; Neienschwander et al, 2008](#)), the next dose is the one with the highest probability of the target TPI (0.20, 0.35), but with a less than 0.25 probability of an excessive or unacceptable TPI.
- If ≥ 1 subject has a DLT at a dose level, then dose escalation cannot occur unless there are 6 or more DLT-evaluable subjects at that dose level. However, if a transient cytokine-release syndrome is reported as the DLT, but resolves within 48 hours and can be managed with prophylactic corticosteroids, the DLRT may decide to escalate the dose with the institution of prophylactic corticosteroid administration.
- The maximum allowed dose increase will be 1 dose level above the maximum of previous evaluated doses.
- Dose escalation can be achieved by evaluating a higher dose level with the same infusion duration (eg, 800 μ g/day for 14 days to 1600 μ g/day for 14 days), or by evaluating the same dose level with a prolonged infusion duration (eg, from 800 μ g/day for 14 days to 800 μ g/day for 28 days). The DLRT may also decide to explore in parallel both options mentioned above after the dose-escalation decision is made, or to prioritize one schedule. In this case, 2 TPI models may be run in parallel to obtain dose recommendations for these 2 schedules separately.
- Intermediate dose levels not pre-specified may be considered based on the optimal dose recommended by the TPI model.

The DLRT is responsible for making the decision to end dose escalation. Generally, the DLRT may consider the modeling of the dose escalation complete if 1 of the following rules is met:

- The highest planned dose level is evaluated and no DLTs occur at any dose level. In this case the maximum administered dose will be used in a dose-expansion cohort.
- The TPI Bayesian model recommends the same dose 3 times (not necessarily sequentially).
- A total of approximately 24 DLT-evaluable subjects have been enrolled.

The Amgen Medical Monitor and Amgen Global Safety Officer can make dose decisions without convening the DRLT in the following limited circumstances:

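### The SAP's list of dose-meeting outputs shows the TPI model only once a DLT has occurred, although the 0.25 overdose limit applies at every dose decision and can bind with no DLTs

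*SAP*

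**What the plan says.** The dosing rule has no DLT condition. Protocol 10.3.1 states that "the next dose is the one with the highest probability of the target TPI (0.20, 0.35), but with a less than 0.25 probability" of lying in the excessive or unacceptable range. Protocol 10.4.2 fixes the timing: "After each cohort, the model's recommended MTD dose for evaluation is the dose with the highest probability of the target TPI". SAP sections 3.1.1.1 and 8 repeat the rule, and section 8 adds: "Dose decision analyses are planned after every 3 to 6 DLT-evaluable subjects are enrolled throughout the dose-escalation cohorts". SAP Appendix C gives the intervals: DLT rates of 0.35 to 0.60 and 0.60 to 1.00 "are defined as excessive and unacceptable, respectively".

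One completion rule in the same sections counts how often the model has recommended the same dose, so it also needs the model to be run at each decision.

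SAP Appendix D lists what the review meeting receives: nine listings and four figures. Only the fourth figure comes from the model: "DLT probability plot at each dose [TPI design if DLT is observed". No interval probabilities appear by name anywhere in that list.

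On cohort size, Protocol 5.1 starts each cohort with three subjects and continues: "In the event that a DLT is observed, 3 additional subjects may be enrolled for a total of up to 6 evaluable subjects". Protocol Table 3 gives 3 to 6 subjects for every escalation cohort without that condition. Protocol 10.3.2 lists repeating or expanding a cohort among the ordinary dosing decisions.

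On the course of the study, Protocol 2.2.4 reports: "As of April 2016, approximately 32 subjects received AMG 211 for up to 6400" µg/day, with no DLT.

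**The concern.** Overdose control is the safety property that Protocol Appendix E and SAP Appendix C claim for this design. It works only if the people choosing the dose see the probability on which it turns. Appendix D, taken literally, gives them no model output until a DLT occurs.

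That would be harmless if the limit could never bind without a DLT. The bracket suggests this belief: with no DLTs, the model is assumed to say only that escalation may proceed. Whether that is so can be computed from the published prior. If the limit can bind in a DLT-free run, Appendix D leaves out the output exactly where the rule has something to say. A DLT-free run is also the situation the protocol reports.

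**Working it through.** **Inputs.** Protocol Appendix E and SAP Appendix C give the model and prior.

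- Model: logit(p) = log a + exp(log b) × log(d / d_max).
- Prior: (log a, log b) bivariate normal with means 0.0536 and −0.1469, standard deviations 1.685 and 1.001, correlation −0.216.
- d_max = 6400 µg/day, the maximum dose named in both appendices.
- Limit: P(p > 0.35) < 0.25, reading excessive and unacceptable together.
- Cohort size 3: the starting size in Protocol 5.1 and the size fixed in the simulations.
- Likelihood with zero DLTs: the product over doses of (1 − p)^n. Cohorts 1 and 2 both enter at 200 µg/day.

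The posterior was obtained by numerical integration over the two parameters. Separate grid and Monte Carlo runs agree to within about 0.003.

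**The plan's own figures first.** Both appendices state P(p ≤ 0.60 at 200) = 0.90; the printed prior gives 0.900. They state P(p ≤ 0.20 at 6400) = 0.21. At d_max this is Φ((log 0.25 − 0.0536) / 1.685) = Φ(−0.855) = 0.196. That is close but not exact, so a recalibrated prior is included below.

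**DLT-free escalation, 3 per cohort.**

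| Completed through | P(p > 0.35) at the next step | P(p > 0.35) at 6400 |
|---|---|---|
| prior only | – | 0.655 |
| 200, 7 days | 0.024 (200, 14 days) | 0.539 |
| 200, 14 days | 0.012 (400) | 0.503 |
| 400 | 0.014 (800) | 0.471 |
| 800 | 0.027 (1600) | 0.432 |
| 1600 | 0.073 (3200) | 0.375 |
| 3200 | **0.273** (6400) | **0.273** |

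The limit never blocks a lower step. It does block the step to 6400. There the excessive part is 0.185 and the unacceptable part 0.088, and 0.185 + 0.088 = 0.273 ≥ 0.25. The eligible dose with the highest target probability is then 3200.

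**Sensitivity of the 6400 step, zero DLTs.**

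- 4, 5 or 6 subjects at 3200, with 3 in each earlier cohort: 0.252, 0.236, 0.222.
- 3 to 6 in each earlier cohort: 0.266 to 0.273 with 3 at 3200, and 0.249 to 0.252 with 4 at 3200. The latter lies on the threshold.
- Cohort 1 left out: 0.272. Cohort 1 entered as 100 µg/day: 0.273.
- Prior mean of log a shifted to −0.0275, so that P(p ≤ 0.20 at 6400) is exactly 0.21: about 0.26 with 3 at 3200.
- d_max read as 12800: 0.07, so 6400 passes.

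**The 12800 step.** The current protocol adds it in section 3.1 and Table 3. After 3 DLT-free subjects at 6400, with 3 per earlier cohort, P(p > 0.35 at 12800) is 0.46 with d_max 6400 and 0.27 with d_max reset to 12800. Both exceed 0.25. With 6 at 6400 the values are 0.36 and 0.22, so the answer then depends on which d_max is used.

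**The case against.** The best defence is that an appendix list of figures does not repeal section 8. Sections 3.1.1.1 and 8 state the rule without condition. SAP 10.5.1.1 says the interval probabilities will be summarised by dose, again without condition. A biostatistics representative sits on the review team (Protocol 10.3.2), and each decision is recorded in a memo (SAP 3.1.1.1). The model could therefore be run and shown outside the list. This stands. It rules out saying that the team never saw the limit, but it does not remove the contradiction between Appendix D and section 8.

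Three stronger readings are tempting, and the documents do not support them.

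- **That the cohort plan and the limit are irreconcilable.** Protocol 5.1 allows three more subjects after a DLT but does not say only then. Table 3 and section 10.3.2 permit larger cohorts with no DLT condition. With 5 or 6 DLT-free subjects at 3200 the limit is met.
- **That a fixed number of subjects at 3200 is needed.** With 4 there, the result falls on either side of 0.25 depending on the earlier cohort sizes.
- **That 6400 was opened against the rule.** Actual cohort sizes are not given, and about 32 subjects had been treated without a DLT. Nothing in the documents shows a breach.

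It can also be argued that 0.25 applies to each interval separately, in which case 6400 passes (0.185 and 0.088). The wording "highest probability of the target TPI (0.20, 0.35), but with a less than 0.25 probability of an excessive or unacceptable TPI" reads more naturally as the two combined.

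**Conclusion.** The inconsistency is real and should be fixed. Appendix D makes the only listed model output depend on a DLT, while the rule it should support applies at every decision. The dependence matters: under the default of 3 per cohort and no DLTs, the overdose probability at 6400 is about 0.27 (about 0.26 with the recalibrated prior) against a limit of 0.25. At 12800, after 3 DLT-free subjects at 6400, it is 0.46 or 0.27 depending on d_max.

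This rests on the printed prior, d_max = 6400 for the 6400 step, the two upper intervals taken together, and 3 DLT-free evaluable subjects at the dose below. The excess at 6400 is modest and disappears with one or two more DLT-free subjects at 3200. The conclusion is that the limit can bind without a DLT, so its output should not wait for one. It does not follow that the limit was ignored in practice, and no view is taken on which dose should have been opened.

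**What to change.** In SAP Appendix D, delete the bracketed condition. At every dose level review meeting, with or without DLTs, table the target, excessive and unacceptable probabilities for each dose and schedule, state the d_max used, and record the model's recommendation in the dose level review memo that SAP 3.1.1.1 already requires.

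The sponsor should reconcile Appendix D with section 8, and the wording of Protocol 5.1 on enlarging a cohort with the 3 to 6 range in Table 3 and the 0.25 limit. No dose or cohort size is proposed here.

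The cost is one line in the SAP and one routine output per meeting. The downside is that the model may hold a dose step until a few more subjects have been observed.
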